The following table summarizes data collection required during the course of the study.

SUBGROUP 2	PRE-OP	SURGERY	IMMEDIATE POST-OP	3 MO	6 MO	1 YR	3 YR	5 YR	7 YR	10 YR
Informed Consent	X									
Demographic	X									

and Historical Record											
Preoperative AKS	X										
Operative Record		X									
Immediate Post-Operative Radiographic Assessment (Bench Mark)			X								
Postoperative AKS (Including ROM)				X	X	X	X	X	X	X	X
Patella Clunk and Crepitus				X	X	X					
EQ5D				X	X	X	X	X	X	X	X
Radiographic Assessment				X	X	X	X	X	X	X	X
Complications & Revisions				Anytime							

SUBGROUP 4	PRE-OP	SURGERY	IMMEDIATE POST-OP	3 MO	6 MO	1 YR	3 YR	5 YR	7 YR	10 YR	
Informed Consent	X										
Demographic and Historical Record	X										
Preoperative AKS	X										
Operative Record		X									
Immediate Post-Operative Radiographic Assessment (Bench Mark)			X								
Postoperative AKS (Including ROM)				X	X	X	X	X	X	X	
Patella Clunk and Crepitus				X	X	X	X	X	X	X	
EQ5D/SF36				X	X	X	X	X	X	X	
Radiographic Assessment				X	X	X	X	X	X	X	
Complications & Revisions				Anytime							

PARTICIPANT EVALUATION SCHEDULES

All study Participants are expected to return for clinical, kinetic and kinematic analysis if any and radiographic evaluation at specific follow-up intervals. The following table summarizes the schedule for post-operative follow-up time intervals:

Evaluation Schedule		
Interval	Follow-Up Window	Months Post-Op Range
Immediate Post-Op	± 2 weeks	Immediate post-op < 2 weeks
3 month follow-up	± 1 month	2-4
6 month follow-up	± 1 month	5-7
1 year follow-up	± 2 months	10-14
3 year follow-up	± 3 months	33-39
5 year follow-up	± 3 months	57-63
7 year follow-up	± 3 months	81-87
10 year follow-up	± 3 months	117 - 123

COMPLICATIONS (ADVERSE EVENTS)

All adverse events, device related (see *Risk Analysis Section*) or non-device related, are to be recorded. Anticipated adverse events are defined, but not limited to, the following:

- Operative side knee manipulations or injections
- Operative side dislocations
- Operative side aspiration of joint fluids
- Falls
- Accidents- motor vehicle, motorcycle, ATV, etc.
- Death
- Any event in which the subject requires hospitalization or outpatient medical attention, including but not limited to: myocardial infarction, cerebral vascular accident, pulmonary emboli, gastrointestinal disorders, or a new diagnosis of a chronic condition (lung disease, renal disease, cancer, diabetes mellitus, hematological abnormalities, etc.).

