RADIOGRAPHIC PROTOCOL

1. **Radiographic Views**
The study requires a standard anteroposterior view, mediolateral view, and a skyline patellar view.
2. **Reviewer**
The study investigator will assess his own patient's radiographs.

3. Assessment Procedure

- Assessments will be recorded on the following two radiographic assessment reports:
 - Form XR100 (immediate post-operative)
 - Form XR200 (6 week, 6 month, 1 year, 3 year, 5 year, 7 year and 10 year).
- The radiographic films will be marked for measurements as described in the following “Measurement angles and reference points” section of this document. These “marked” radiographs will be used to determine the implant femoral flexion angle (α), tibial angle (β), total valgus angle (Ω), tibial angle (σ), and femoral flexion (γ).
- The immediate post-operative film will be used as an index for subsequent follow-up assessments.

The radiographic assessment definitions are as follows:

- Anteroposterior Radiograph:
This radiographic view can be obtained with the participant in the standing or recumbent position.
- Mediolateral Radiograph:
This radiographic view can be obtained with the participant in the standing or recumbent position.
- Skyline Radiograph:
This radiograph view can be obtained with the patello-femoral joint in flexion
- Radiolucency or Radiolucent Lines:
A radiographic clearing or line not exceeding 2mm in width at the bone/cement or cement/implant interface
- Osteolysis:
A progressive radiolucency > 2mm in **two or more** zones not present on immediate postoperative radiographs and/or a bony destructive lesion that is progressive in nature.
- Migration/Subsidence:
A component migration of > 3 mm or > 3° as compared to immediate post-operative radiographs is considered a failure.

DATA COLLECTION

All sites will be required to complete and submit case report forms on Biomet’s online database, Joint Assist 2.0, in a timely manner. Forms will be monitored for completeness and accuracy.

Further, it is imperative that the investigator answers all questions on the case report forms. All data should be accurate, indelible, legible, dated on the date of entry, and signed by initials, and/or formal signature by the authorized personnel documenting the data.

MONITORING PLAN

Prior to commencing the study the Monitor will provide the investigators with the necessary information to enable him/her to carry out his responsibilities. This information includes but not limited to:

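### AP and mediolateral films may be standing or recumbent with no stated matching to the index film, so apparent migration near the 3 mm / 3° failure threshold may partly reflect projection

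*Combined protocol and SAP*

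**What the plan says.** All the radiographic rules are in the Radiographic Protocol of the combined protocol and SAP, under Assessment Procedure and the definitions that follow it.

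- **Position.** The same sentence stands under the AP view and under the mediolateral view: "This radiographic view can be obtained with the participant in the standing or recumbent position". The skyline view has its own sentence, which mentions flexion only: "This radiograph view can be obtained with the patello-femoral joint in flexion".
- **Reference film.** "The immediate post-operative film will be used as an index for subsequent follow-up assessments". The Participant Evaluation Schedules table times this film as "Immediate post-op < 2 weeks".
- **Failure rule.** "A component migration of > 3 mm or > 3° as compared to immediate post-operative radiographs is considered a failure".
- **Measurements.** Films are marked to obtain five angles (α, β, Ω, σ, γ). The protocol points to a section on measurement angles and reference points, which the public text does not reproduce. Forms XR100 and XR200 are not reproduced either.
- **Reader.** "The study investigator will assess his own patient's radiographs".

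The Endpoints table lists radiographic assessment as secondary, at all follow-up visits, in both subgroups.

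**The concern.** The failure rule compares two films against a small absolute threshold. Such a comparison is cleanest when the films are taken alike. Here the protocol expressly permits two positions and, in the public text, neither ties follow-up films to the index position nor asks for position to be noted.

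A radiograph is a two-dimensional projection. Limb rotation, knee flexion and magnification can differ between a standing and a recumbent film, and each can alter a measured angle or distance when the component has not moved. The error can go either way: a stable component may appear to have migrated, or true migration may be partly hidden.

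Two features add to this. One index film serves every later comparison (seven visits on the list for Form XR200), so an unrepresentative index carries through all of them. And if position is not recorded, it cannot be examined or adjusted for after ten years of follow-up.

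**Working it through.** **The plan's own figure.** There is none to reproduce: the documents give no error rate, event count or sample size for migration. The sample-size calculations concern range of motion (ROM) and the American Knee Society score (AKS) and do not depend on this point.

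**The passages side by side.**

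1. Position is optional for the AP and mediolateral views. The skyline view is not covered by that option.
2. The threshold applies to component migration, that is, movement of a component relative to its bone, and both appear on the same film. The text does not say that a change in any of the five angles is a failure.
3. Total valgus (Ω) is the whole-limb angle and the one most directly affected by loading; it is not named as a migration measure. Component-to-bone measurements would be affected only indirectly, through rotation, flexion or magnification.
4. The public text describes no allowance for measurement error, repeat film or second read.

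So the permission and the threshold do meet in the same comparison, but the documents do not show how far position moves the relevant measurement.

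**How the result depends on what is unknown.** Take one angle, one index-to-follow-up comparison and no true migration. Let s be the error SD per film and b the apparent shift caused by a change of position. Both are assumptions; the documents give neither. The difference D between films is Normal with mean b and variance 2s², so

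P(|D| > 3°) = 1 − Φ((3 − b)/(s√2)) + Φ((−3 − b)/(s√2)).

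With s = 1.0° and b = 1°, s√2 = 1.414, and the probability is 1 − Φ(1.414) + Φ(−2.828) = 0.081.

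| Assumed s | b = 0° | b = 1° | b = 2° |
|---|---|---|---|
| 0.5° | 0.0% | 0.2% | 7.9% |
| 1.0° | 3.4% | 8.1% | 24.0% |
| 1.5° | 15.7% | 20.3% | 32.8% |

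On the 250 knees per group planned for subgroup 2, the middle row is 250 × 0.0339 = 8.5, 250 × 0.081 = 20 and 250 × 0.24 = 60 knees, if every knee changed position.

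The b = 0° column is what measurement error alone produces. Only the excess over it belongs to film position, and that excess is zero if position does not shift the measurement. The table shows sensitivity to assumptions; it does not estimate this trial's error rate. It does not address the 3 mm limb.

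**Where it acts.** Subgroup 2 is randomised, so a position effect is mainly noise unless position differs by arm. Subgroup 4 uses a historical/concurrent control, with its sites and start still to be settled. A difference in positioning between the cohorts would not be balanced by randomisation there.

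**The case against.** The strongest reply is that the rule concerns component migration. An investigator who judges an apparent shift to be projection is not obliged to call it migration. The measurement section and the two forms, which the public text lacks, might standardise projection or already record position. The outcome is secondary, and nothing in the documents suggests that positioning habits will differ between cohorts.

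Most of this stands as a limit on the point. It does not remove it: leaving the judgement to an investigator reading his own patients' films is no substitute for comparable films, and the permission for either position is explicit.

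A reader might infer more than the documents support:

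- *That exceeding 3° on any one of five angles is a failure, giving a very high false-failure rate.* The protocol states no such rule. The calculation would also need the angles to be independent, although several are read from the same film and all share one index, and it would need error SDs that the documents do not give.
- *That index films will usually be recumbent and later ones standing.* The schedule gives only the timing of the index film.
- *That survivorship or the primary analyses are affected.* The text does not link this radiographic failure to survivorship or revision, and the primary endpoints are ROM and AKS at 1 year.
- *That only films in matched positions should count.* Such a rule could discard true migration seen on a mismatched film.

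**Conclusion.** The point holds as a gap in standardisation. Either position is allowed for AP and mediolateral films, the public text requires neither matching nor recording, and a fixed 3 mm / 3° threshold is applied to the comparison with the index film. Changes near that threshold may therefore be partly a matter of projection.

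Its size cannot be stated from the documents. It runs from nothing, if position does not shift the measurement that defines migration, to a material excess if the shift is a degree or two. The primary analyses and the sample size are untouched.

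The conclusion assumes that the unreproduced measurement section and forms do not already require one position per patient. The possible bias in subgroup 4 is conditional on positioning differing between the cohorts. The case for acting is that the remedy is cheap now, whereas unrecorded positions would be hard to recover later.

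**What to change.** Replace the two sentences that allow either position with wording such as: *Each patient's AP and mediolateral follow-up films are taken in the same position as that patient's index film where feasible. The position is recorded with each film.* Record it on XR100 and XR200 if those forms do not already have the field.

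Add one analysis sentence: *A change of more than 3 mm or 3° seen on films in different positions is kept in the analysis and flagged. Migration failure is reported with and without flagged films as a sensitivity analysis.*

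The cost is a few sentences, at most one form field and one extra tabulation, with no additional films. Sites lose the freedom to vary position within a patient, and where the index film was recumbent, matched follow-up films would not be weight-bearing. Matching position also does not by itself control rotation or flexion, so it reduces the problem without removing it.

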A PROSPECTIVE CONTROLLED MULTI-CENTER STUDY ON VANGUARD™ COMPLETE KNEE & VANGUARD™ HIGH FLEX RP KNEE

GENERAL INFORMATION

Principal Investigators

[name]., Ph.D. – 75 Cases
[name]., Ph.D. – 75 Cases
[name] [name]., Ph.D. – 75 Cases
[name]., Ph.D. – 75 Cases

Principal investigators are responsible for the overall project and performing the surgical procedures in all study groups. Responsible for applying for ethical and management approval, recruitment of patients, obtaining patient consent, managing postoperative care of patients and adverse event reporting.

Study Sponsor

Biomet Korea

Study sponsors take responsibility for initiation, management, and/or financing of a clinical studies at investigational sites.

Study Monitor in Korea

[name]

Study monitors are responsible for carrying out the monitoring procedure as indicated in the protocol.

STUDY OBJECTIVE

The primary objectives of this clinical study include:

- Evaluate size fit and long term performance of Vanguard Complete Knee (“Fixed”) System in Asian and Latino population Compare Vanguard High Flex Rotating Platform (“High Flex”) Knee System to Vanguard Complete Knee System in Asian population in terms of:
 - Early ROM
 - Clinical outcomes
- Compare current design to new design of Vanguard High Flex Rotating Platform Knee System in terms of :
 - Early ROM
 - Clinical outcomes

DEVICE DESCRIPTION

Vanguard Complete Knee

Vanguard Knee is a metal and polyethylene system designed to replace the body's natural knee joint and is indicated for cemented tibial and cementless femoral use. The system contains three (3) primary components and one (1) peripheral component. The primary components include, femoral, tibial, and bearing components, while the peripheral component is the patella button. The use of the patella button is optional.

Vanguard High Flex Rotating Platform Knee (current design)

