Vanguard High Flex RP knee is an extension to the existing Vanguard Knee and has been specifically designed to facilitate greater than 135 degrees of knee flexion as required by certain patients. Specifically the Vanguard High-Flex Knee components are required to be able to flex to 150° without point loading or falling off the back of the tibia and to be hyper extended to 15°. It should be noted that this range of motion would only be obtained where the patient had similar flexion and hyperextension ability prior to the arthroplasty. The decision on which rotating platform variant to use is at the discretion of the operating surgeon

Mobile bearing knees are considered advantages as they enable improved congruency between the femoral component and the bearing, compared with a fixed bearing, which results in lower contact stresses of the bearing, thereby reducing wear. Another advantage of mobile bearings is the ability for self-alignment, which reduces wear caused by mal-alignment, enabling the knee to function more naturally and prevents torsion stress on the implant/bone cement/bone interface which may cause loosening.

The tibial tray of the High Flex knee is available in 9 sizes, from 59 to 91mm in 4 mm increments, in interkok finish for cemented applications or with porous plasma sprayed titanium coating for cementless use. It is manufactured from cast cobalt chromium alloy. The stem has a tapered cone geometry for press fit stability. In the cementless option the proximal 1/3 of the stem is porous coated with plasma sprayed titanium. (Note: The tibial trays are manufactured and CE marked by Biomet Spain).

The femoral component is offered in thirteen sizes from 55 to 80mm in 2.5 mm increment, it is anatomic in design (i.e. right and left). It is manufactured from cast cobalt chromium alloy.

The bearing is compression moulded UHMPWE (ArCom). It is matched to the femoral component and is available in 5 thickness from 10-18mm (2mm increments) and 13 sizes from 50mm to 80mm (2.5mm increments). The bearing was designed specifically for the High-Flex to allow rotation of ±8° without overhang.

The patella has an anatomic design and is matched to the thirteen sizes of femoral component patella tracks. It is available in one thickness only. It is compression moulded from UHMWPE (ArCom). Use of the patella button is optional at the discretion of the surgeon.

STUDY DESIGN

[figure not shown]

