Exclusion Criteria

In accordance with Absolute and Relative Contraindications for use for Vanguard Complete Knee System and Vanguard High Flex Rotating Platform Knee System.

Absolute contraindications include: infection, sepsis, osteomyelitis, and failure of a previous joint replacement.

Relative contraindications include:

- A. Uncooperative patient or patient with neurologic disorders who are incapable of following directions,
- B. Osteoporosis,
- C. Metabolic disorders which may impair bone formation,
- D. Osteomalacia,
- E. Distant foci of infections which may spread to the implant site,
- F. Rapid joint destruction, marked bone loss or bone resorption apparent on roentgenogram,
- G. Vascular insufficiency, muscular atrophy, neuromuscular disease,
- H. Incomplete or deficient soft tissue surrounding the knee.

ENDPOINTS

	SUBGROUP 2	SUBGROUP 4
PRIMARY ENDPOINTS*	Range of Motion at 1 yr postop. AKS at 1 year postop	Range of Motion at 1 yr postop. AKS at 1 year post op
SECONDARY ENDPOINTS	At all follow-up visits: Survivorship American Knee Society Score. Range of Motion Radiographic Assessment Patient Satisfaction – EQ5D Complications including revisions Patella Clunk and Crepitus	At all follow-up visits: Survivorship American Knee Society Score. Range of Motion Radiographic Assessment Patient Satisfaction – EQ5D - OKS - FJS Complications including revisions Patella Clunk and Crepitus

*For sample size calculations.

PARTICIPANT POPULATION (SAMPLE SIZE)

Participant population is determined based on primary/secondary endpoints of each subgroup following superiority or non-inferiority methodologies. Minimum sample sizes are determined in order to prove the hypotheses.

Subgroup 2 - Primary Endpoint Range of Motion at 1 year postoperative
 Superiority test

Null Hypothesis: H_0 $\mu_t = \mu_c$

Alternative Hypothesis: H_a $\mu_t = \mu_c + d$

μ_t : mean of ROM in the trial group (Vanguard Complete Knee) at 1 year postoperative.

μ_c : mean of ROM in the control group (VG RP Knee) at 1 year postoperative.

$\alpha = 0.025$ Significance Level (95% confidence)

$\beta = 0.20$ 80% Power

$d = 5$ (degrees) Clinically Relevant Difference in ROM based on literature and engineering input.

$\xi = 17.5$ Estimate standard deviation of ROM at 1 year postoperative. This value is based on results (preop and 1 year postop) from literature¹

$N = 231$

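### The radiolucency and osteolysis definitions conflict at 2 mm and omit the bone/implant interface, leaving some wide lines and thin lines at cementless components without a category

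*Combined protocol and SAP*

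**What the plan says.** The definitions stand in the Radiographic Protocol section, under Assessment Procedure. A radiolucency or radiolucent line is "A radiographic clearing or line not exceeding 2mm in width at the bone/cement or cement/implant interface". Osteolysis has two alternative parts. The first is "A progressive radiolucency > 2mm in" at least two "zones not present on immediate postoperative radiographs and/or a bony destructive lesion that is progressive in nature"; the second is the destructive lesion named at the end of that quotation. Migration has its own rule: "A component migration of > 3 mm or > 3° as compared to immediate post-operative radiographs is considered a failure".

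On fixation, the Device Description says the Vanguard Complete Knee is "indicated for cemented tibial and cementless femoral use". The High Flex RP tibial tray is offered "in interkok finish for cemented applications or with porous plasma sprayed titanium coating for cementless use". Fixation of the High Flex femoral component is not stated.

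The Endpoints table lists radiographic assessment as a secondary endpoint at all follow-up visits in both subgroups. It names no radiolucency variable.

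**The concern.** Two features of the radiolucency definition do not fit the rest of the protocol.

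The first is width. The definition stops at 2 mm, and the osteolysis definition then uses the same word for something wider than 2 mm. If the intent was a split at 2 mm, the two halves do not meet. Osteolysis adds conditions on zones, progression and the index film, and a wide line that fails any of them drops out of both categories. A 1.5 mm line at a cement interface is classified, while a 3 mm line in a single zone may not be.

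The second is interface. Only bone/cement and cement/implant are listed. A cementless component has neither, yet the protocol describes cementless components in both devices. For the Complete Knee femur, cementless use is the use described, not an exception.

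At stake is whether radiographic findings are complete and comparable between arms over 10 years of follow-up. Each investigator reads his own patients' films, so sites may resolve the gap differently. Subgroup 4 also reuses the subgroup 2 High Flex arm as its control, so a change in fixation mix could be mistaken for an effect of the new design.

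**Working it through.** The plan gives no figure to reproduce, and no sample size, power or event calculation is involved. The check applies the definitions literally to each kind of finding.

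Inputs, from the Radiographic Protocol:
- Radiolucency: width up to 2 mm, cement interfaces only.
- Osteolysis, first part: over 2 mm, progressive, two or more zones, absent from the index film. No interface is named.
- Osteolysis, second part: a progressive destructive bone lesion, with no condition on width, number of zones or interface.

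| Case | Interface | Width | Zones | New and progressive | Category under the text |
|---|---|---|---|---|---|
| a | cement | ≤2 mm | any | either | radiolucency |
| b | cement | >2 mm | 2 or more | yes | osteolysis, first part, although a radiolucency is said not to exceed 2 mm |
| c | cement | >2 mm | 1 | either | none, unless osteolysis by the second part |
| d | cement | >2 mm | 2 or more | no | none, unless osteolysis by the second part |
| e | bone/implant | ≤2 mm | any | either | none, unless osteolysis by the second part |
| f | bone/implant | >2 mm | 2 or more | yes | osteolysis, first part, on a plain reading |
| g | bone/implant | >2 mm | 1, or more but not both new and progressive | as stated | none, unless osteolysis by the second part |
| h | any | any | any | progressive destructive lesion | osteolysis, second part |

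The gaps are c, d, e and g. Case b is the contradiction in wording. Case f would also be lost if the cement-only restriction were carried over from the radiolucency definition, but the osteolysis text does not say that it is.

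Setting this against the Device Description:
- Complete Knee: the femur is cementless (cases e to g can arise) and the tibia is cemented (cases a to d).
- High Flex RP: the tray may be either, and femoral fixation is not stated.

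The arms may therefore differ in how many findings fall into the gaps. Neither the direction nor the size can be worked out, because the documents give no lucency rate for any interface and no proportion cemented in either arm.

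**The case against.** The strongest reply is that this is loose drafting, not a contradiction that would stop an assessor. On a sensible reading, up to 2 mm is a radiolucent line, and over 2 mm, progressive and in several zones is osteolysis. That is probably the intent, and it makes case b workable. It does not close cases c, d, e or g.

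A second reply is that the serious findings are captured anyway. This largely stands. A reader might infer that no lucency at a cementless component, and no wide single-zone line, can ever be counted. The text does not support that. The first part of osteolysis names no interface, the second part has no width, zone or interface condition, and migration is counted whatever the fixation. However, the second part requires a judgement of progressive destruction, so it does not reach stable or non-destructive lines.

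A third reply is that forms XR100 and XR200, and the section on measurement angles and reference points, may already record zones, widths or bone/implant lines. They are not in the text available, so this can be neither confirmed nor excluded. It limits what can be said about actual recording, but the written definitions remain as they are.

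Finally, no radiolucency hypothesis or test is specified, and the primaries are untouched. That is correct and limits the weight of the point.

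**Conclusion.** The point holds in this limited form. The definitions are inconsistent at 2 mm. Lines over 2 mm that fail the first part of osteolysis have no category unless judged progressive destructive lesions. Lines up to 2 mm at a bone/implant interface fall outside the radiolucency definition, although both devices are described with cementless components.

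The effect is confined to the secondary radiographic endpoint. The 1-year ROM and AKS primaries and the sample size do not depend on it. A reader might also infer that survivorship is affected. The documents do not support this: migration is the only radiographic finding called a failure, and complications and revisions are collected separately at any time.

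No magnitude can be given. It is tempting to say that if a share p of one arm is cementless and the other arm is fully cemented, recorded lucency falls to 1 − p of its true relative rate. That requires equal true rates, a fully cemented comparator and no countable lucency at any cementless component. The documents give no basis for the first two, and cases f and h rule out the third.

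The conclusion assumes that assessors apply the definitions as written and that the unseen forms do not already fill the gap. The correction is worth making because it costs little now, whereas a later one could mean re-reading up to 10 years of films.

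**What to change.** Redefine radiolucency as a line at the bone/cement, cement/implant or bone/implant interface, recorded by zone and by maximum width (≤2 mm, >2 mm). Removing the width cap resolves the conflict with the osteolysis wording. It also means that lines over 2 mm that do not meet the osteolysis definition are still counted.

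Leave the osteolysis definition unchanged, including the condition that the finding is absent from the immediate post-operative film; dropping that condition would broaden the definition and weaken the index-film comparison. Report lucency by component fixation within each arm.

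The cost is a revised definition and one added breakdown in the tables. Forms XR100 and XR200 may need a small change if they do not already capture interface, zone and width. Reported lucency rates may rise slightly.
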